#### ***4.5.6 Vital Signs, Physical Findings, and Other Observations Related to Safety***

##### ***4.5.6.1 Vital Signs***

Vital sign parameter measurements (including weight over time) will be summarized by treatment group within each study part, pooled treatment groups, and over all subjects combined. Descriptive statistics will be presented for results and change from baseline at each visit where parameters were scheduled to be collected.

##### ***4.5.6.2 12-Lead Electrocardiogram***

Twelve-Lead ECG interval parameters will be summarized by treatment group within each study part, pooled treatment groups, and over all subjects combined. Descriptive statistics will be presented for observed values and changes from baseline at each visit where parameters were scheduled to be collected.

Twelve-lead ECG will be classified by the investigator as “normal,” “abnormal, not clinically significant,” or “abnormal, clinically significant.” Three-by-three contingency tables will be presented to summarize the shift from the baseline category to the worst post-baseline value. Summary results will include the count and percentage of subjects within each shift category and treatment groups presented.

Prolonged corrected QT (QTc) intervals including the corrected QT interval using Bazett's formula (QTcB) and the corrected QT interval using Fridericia's formula (QTcF) will be summarized as QTc measurements (msec) that are >450, >480, and >500 at each visit where ECG is routinely collected per the clinical study protocol. Change from baseline categories will also be summarized for measurements that represent a change >30 or >60 relative to the baseline value. Summary results will include the percentage of subjects within each category and treatment groups presented.

#### *4.5.6.3 Physical Examination*

Any clinically significant abnormalities with onset prior to signing of the ICF will be recorded on the Medical History form and recorded on the Adverse Events form if onset is after signing of the ICF. A separate subject listing of physical examination results will not be provided.

#### *4.5.6.4 Prior and Concomitant Medications*

Medications will be coded using the WHO Drug Global B3, version March 1, 2023. Medications entered on the eCRF will be mapped to ATC drug class (level 2) and preferred name.

Prior and concomitant medications will be determined programmatically based on medication start and end dates. A prior medication is defined as any medication administered prior to the date of the first dose of study drug. A concomitant medication is defined as any medication administered on or after the date of the first dose of study drug. A medication may be defined as both prior and concomitant. If it cannot be determined whether a medication was received prior to the start of study drug dosing due to partial or missing medication start and/or end dates, it will be considered a prior medication. Likewise, if it cannot be determined whether a medication was received after the start of study drug dosing, it will be considered concomitant.

For concomitant medications summaries, the number and percentage of subjects receiving any medication will be summarized treatment group within each study part, pooled treatment groups, and over all subjects combined, as will the number and percentage receiving any medication by ATC drug class and preferred name. Subjects reporting use of more than one medication at each level of summarization (any medication received, ATC class, and preferred name) will be counted only once. ATC class terms will be displayed by descending order of incidence, as will preferred names within each ATC class. The study phase during which each medication was received (e.g., prior, concomitant, or both) will be presented on the listing of prior and concomitant medications.

Subjects may use a second generation H1AH that is different from background therapy as rescue medication if symptoms worsen, as needed. Rescue medications will be reported on the Prior and Concomitant Medications eCRF. While rescue medications may be initiated during the Screening period of study participation (see [Section 3.3.1.2](#)), summary of rescue medications for analysis will include those medications initiated on or after the first dose of study drug that were reported with an indication labelling the medication as a “rescue” treatment. The number and percentage of subjects initiating a rescue medication at any time after study treatment initiation as well as those initiating

a rescue medication during the Double-Blind Treatment Period or Safety Follow-Up Period, specifically will be summarized by treatment group within each study part, pooled treatment groups, and over all subjects combined. Additionally, the number and percentage receiving a rescue medication by preferred name will be provided for each study period (Double-Blind Treatment Period versus Safety Follow-Up Period). Any subjects that require the use of a rescue medication will also be presented in a listing.

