#### ***3.3.1.2 Rescue Medications***

In addition to their daily background therapy, for the duration of the study (Screening, Double-Blind Treatment, and Safety Follow-Up Period), if symptoms worsen, all subjects will be able to use a second generation H1AH that is different from background therapy as rescue medication as needed. The choice of H1AH and dosage will be determined by the Investigator; however, discussion with the subject prior to initiation of any rescue medication is encouraged. Once a rescue medication has been selected,

switching to a different rescue medication during the study is not permitted. Use of rescue medication must be documented.

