Baseline characteristics will be summarized by treatment group within each study part, pooled treatment groups, and over all subjects combined for the Safety Analysis Set, Full Analysis Set, and PK Set (to include applicable EP262 treatment groups only).

Prior CSU therapies will be coded using the World Health Organization (WHO) Drug Global B3, version March 1, 2023. Medications entered on the eCRF will be mapped to Anatomical Therapeutic Chemical (ATC) drug class (level 2) and preferred name. The number and percentage of subjects receiving any prior CSU therapy will be summarized by treatment group, as will the number and percentage receiving any medication by ATC drug class and preferred name. Subjects reporting use of more than one medication at each level of summarization (any medication received, ATC class, and preferred name) will be counted only once. ATC class terms will be displayed by descending order of incidence, as will preferred names within each ATC class.

Medical history conditions will be mapped to preferred terms and system organ classes using the Medical Dictionary for Regulatory Activities (MedDRA, version 26.0). Frequency counts and percentages to summarize subjects reporting medical history by system organ class and preferred term will be presented.

A summary of background therapy medications (as described in [Section 3.3.1.1](#)) will be provided. Background therapies include CSU therapies reported on the Prior CSU Therapy eCRF with an ongoing end date or an end date that continues through first dose of study drug). The number and percentage of subjects reporting a background H1AH will be determined as any medication reported in the ATC level 2 of "ANTIHISTAMINES FOR SYSTEMIC USE."

The number and percentage of subjects receiving any background therapy will be summarized by treatment group, as will the number and percentage receiving any H1AH background medication by preferred name. In addition, a summary of any "other" background therapy medications will also be provided and summarized by preferred name. The summary of "other" background therapy medications will include

any CSU therapies ongoing at the initiation of study treatment that are not captured in the ATC level 2 of “ANTIHISTAMINES FOR SYSTEMIC USE.” A listing of qualifying background therapy medications will be provided.

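### The by-arm rescue summary counts only rescue drugs started on or after first dose, so a rescue record opened in Screening and still running on treatment is left out

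*SAP*

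**What the plan says.** SAP 3.3.1.2 and Protocol 8.5.2 allow a second-generation H1 antihistamine as rescue "for the duration of the study (Screening, Double-Blind Treatment, and Safety Follow-Up Period), if symptoms worsen". Protocol 8.5.2 adds that the rescue drug, once chosen, stays the same for the rest of the study.

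SAP 4.5.6.4 sets the analysis rules:

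- On the source: "Rescue medications will be reported on the Prior and Concomitant Medications eCRF".
- On what enters the summary: the "summary of rescue medications for analysis will include those medications initiated on or after the first dose of study drug", if labelled as rescue. The same sentence acknowledges that rescue may begin in Screening.
- On the main count: "The number and percentage of subjects initiating a rescue medication at any time after study treatment initiation". The counts for the Double-Blind Treatment and Safety Follow-Up Periods are worded the same way and shown by treatment group.
- On drug names: "Additionally, the number and percentage receiving a rescue medication by preferred name will be provided for each study period".
- On listings: "Any subjects that require the use of a rescue medication will also be presented in a listing".
- On general classification: "A medication may be defined as both prior and concomitant".

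Protocol 16.9 plans a summary of rescue use and sets no start-date limit. Protocol 16.2 and SAP 4.4.3 name use of rescue medication as an intercurrent event, handled by treatment policy.

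**The concern.** The planned count measures new starts, whereas the Protocol's plan and the intercurrent event are both expressed as use. The two differ when a drug begun in Screening is carried across first dose. The design leaves room for that: Screening lasts from 2 weeks to 30 days, rescue is open to every subject throughout it, and the drug cannot later be replaced by another rescue drug that would produce a new start date.

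At stake is the description of on-treatment rescue by arm. Under treatment policy, the UAS7 difference includes whatever rescue did in each arm, so a reader will look at the rescue table to interpret it. Starting rescue in Screening precedes randomization, but continuing or stopping it afterwards does not, and that can differ between arms. The present count cannot show it.

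**Working it through.** No figure in the plan is at issue, so the check is of the rule itself.

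**Definitions.** For each rescue-labelled record let S be the start day and E the end day (open if ongoing). First dose is Day 1 and the nominal Week 6 visit is Day 43 (Protocol Appendix A).

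- Present rule (SAP 4.5.6.4): count the subject if any record has S ≥ Day 1.
- Overlap rule for the Double-Blind Period: count the subject if any record has S ≤ Day 43 and E ≥ Day 1.

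**Rule check on hypothetical dates (not trial data).**

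| Case | Rescue records | Present rule | Carried-over row | New-start row |
|---|---|---|---|---|
| A | One record: Day -10, ongoing at Day 43 | 0 | 1 | 0 |
| B | Two records: Day -10 to Day -9; Day 12 to Day 14 | 1 | 0 | 1 |
| C | One record: Day -10 to Day -9 | 0 | 0 | 0 |

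Case A is excluded because -10 < 1, although the same SAP section would class the record as both prior and concomitant. Case B is counted because 12 ≥ 1. Case C is rightly left out under either rule. A subject who took rescue on Days 12 to 14 could be recorded as A or as B, and so adds 0 or 1 to the Double-Blind count depending only on how the record was kept.

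**Size.** The overall undercount in an arm is

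U = number of subjects with a rescue record where S < Day 1 and E ≥ Day 1, and with no rescue record where S ≥ Day 1.

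The documents give no rescue rate and no dating convention, so U cannot be evaluated. U = 0 if each course is dated separately or if no Screening record stays open. If the planned arm sizes in SAP 4.6 are the denominators, each such subject lowers the reported percentage by 1/38 = 2.6 points (50 mg or 150 mg), 1/30 = 3.3 points (25 mg) or 1/48 = 2.1 points (pooled placebo).

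**Other visible outputs.** The concomitant-medication table would show the Case A drug by arm under its class and preferred name, but without a rescue label, so it cannot be read as a rescue count. The rescue listing has no start-date limit and should show the subject, but a listing gives no counts by arm.

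**The case against.** The strongest answer is that the rule is deliberate. The sentence mentions Screening starts and then selects later ones, and new rescue after treatment begins is a legitimate measure. Protocol 16.9 sets no numerator, so the SAP narrows it rather than contradicts it. This stands as far as it goes: the rule is a disclosed choice, and the proposed change keeps its count. It does not answer the point that continued use is then missing from the arm-level rescue figures.

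Second, the undercount depends on eCRF completion practice that the documents do not give. Protocol Appendix A asks sites to record any rescue use and reviews medications at every visit, which leans towards recording actual use. That does not settle how courses are dated, so the point stays conditional.

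Third, an as-needed record left open does not show that a tablet was taken on treatment. This stands, and limits what a carried-over row can claim.

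Fourth, the information survives in the concomitant-medication table and listings. True, but neither gives a rescue count by arm. The exploratory sections are blacked out, so another rescue output cannot be ruled out.

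Two stronger readings are tempting. A reader might infer that the SAP is inconsistent because its background-therapy table includes drugs continuing through first dose. That table describes baseline treatment, and a different purpose justifies a different date rule. A reader might also infer from the shift between initiating and receiving that two different numerators are planned. If the start-date limit governs the whole rescue summary, as the text suggests, only the wording is unclear.

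**Conclusion.** The point holds in a limited form. Under the stated rule, a rescue record that begins in Screening, continues on or after first dose and is followed by no later start is left out of the visible by-arm rescue counts. The size is unknown and may be zero.

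A reader might infer that on-treatment rescue is certainly understated. The documents do not support that without the dating practice. A reader might also infer that the primary result is biased. It is not: rescue is handled by treatment policy, the MMRM uses the observed UAS7 whatever the rescue status, and this table does not feed the model. The consequence is confined to how well a reader can describe on-treatment rescue by arm when interpreting the UAS7 difference. This makes it an optional improvement.

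**What to change.** In SAP 4.5.6.4, report by arm and study period the subjects with any rescue-labelled record overlapping the period, in separate rows:

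- (a) carried over from Screening;
- (b) newly initiated on or after first dose, which keeps the sponsor's present count.

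Use the same numerator for the by-preferred-name rows. A subject with both kinds of record appears in both rows and once in any total. In Safety Follow-Up, row (b) matches the present count only if limited to starts within that period, so records begun on treatment and still open there should be labelled separately. Footnote row (a) as records ongoing in the period rather than confirmed use.

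The cost is two or three sentences and date logic in one table, using the start and end dates with which the SAP already classes medications as prior or concomitant. The downside is that row (a) may include subjects who took no rescue in the period; the split and the footnote disclose this. Patient care and the primary analysis do not change.

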#### **4.6 Determination of Sample Size**

The study will enroll approximately 154 subjects.

In Part 1, approximately 114 subjects will be randomized in a 1:1:1 ratio to receive 50 mg of EP262, 150 mg of EP262, or placebo.

In Part 2, approximately 40 subjects will be randomized in a 3:1 ratio to receive 25 mg of EP262 or placebo.

Overall, approximately 30, 38, 38, and 48 subjects will be randomized to receive 25 mg EP262, 50 mg EP262, 150 mg EP262, and placebo, respectively, across both parts of the study.

For Part 1, a sample size of 34 subjects per treatment group will provide 80% power to detect an 8-point difference in the UAS7 change from baseline at Visit 4 (Week 6), assuming a standard deviation of 13 points, and a 2-sided alpha of 10%.

For Part 2, a sample size of 27 subjects receiving 25 mg of EP262 and 43 subjects receiving placebo pooled from both parts of the study will provide 80% power to detect an 8-point difference in the UAS7 change from baseline at Visit 4 (Week 6) between EP262 25 mg and placebo, with the same assumption of 13-point standard deviation and 2-sided alpha of 10%.

#### **4.7 Changes in the Conduct of the Study or Planned Analyses**

Section 16.8.3 of the clinical study protocol defines the following planned primary and sensitivity analysis to address missing data in the primary analysis:

The primary analysis of the primary endpoint of change from baseline in UAS7 will include all observed data (weekly UAS7 scores considered non-missing) with no data imputations, under the assumption of missing at random.

As a sensitivity analysis, the primary endpoint will also be analyzed with multiple imputation procedures. The SAP will provide full detail of the methodologies that will be used.

Section 16.1 of the clinical study protocol defines the Per Protocol Set as: The Per Protocol (PP) Set is a subset of the FAS containing subjects who meet study eligibility requirements and had no protocol deviations that might impact the assessment of efficacy and/or PD measurements. Subjects will be analyzed according to randomized treatment assignment. The PP Set will be used for sensitivity analyses relating to efficacy and/or PD. The type of protocol deviations governing exclusion from the PP Set will be determined prior to database lock and will be detailed in the SAP.

Section 16.8 states the following additional analysis on efficacy and/or PD endpoints: For select endpoints, percent change from baseline will also be summarized.

The protocol-defined sensitivity and supplemental analyses will not be conducted for this study and percent change from baseline will not be summarized. In addition, a Per Protocol Set will not be determined.

Section 16.8.2 of the clinical study protocol defines the following planned additional efficacy analyses:

Efficacy endpoints that are defined as continuous variables will be analyzed using a similar model as described for the primary efficacy endpoint if they are collected at multiple post-baseline visits; otherwise, they will be analyzed using analysis of covariance (ANCOVA) adjusted for randomization strata and baseline measurements of the response parameter of interest. For continuous endpoints that do not meet the normal distribution assumption, they will be analyzed by stratified Hodgens-Lehmann estimates for the median, with the 90% confidence intervals derived using stratified Van-Elteren test. Other endpoints defined as response proportions will be analyzed using a Cochran-Mantel-Haenszel test stratified by randomization strata. Time-to-event data will be analyzed using a Cox regression model, stratified by randomization strata.

No hypothesis testing will be conducted for secondary and exploratory endpoints; only descriptive analysis results will be provided. Given the limited sample size and the nature of Phase 2 as a proof-of-concept (POC) study, hypothesis testing for secondary endpoints may not be considered appropriate and has been excluded from the SAP.

In addition, supplemental evaluation of normality assumptions and use of the stratified Hodgens-Lehmann and stratified Van-Elteren test (as needed) will not be utilized. Given the sample size of the study, the estimates are assumed to be valid based on Central Limit Theorem, even if select data are not normal.

